2. **For laboratory visit outcomes**, we will again utilize multilevel models (with 10 labs per person—5 per condition—nested within individuals; two-level models). A two-level model will predict each repeated measures lab outcome from covariates (daily pain, illness, PRN medication use) and the interaction between (1) **experimental condition** (a dichotomous variable coded as 0 for natural hormone withdrawal condition and 1 for hormone stabilization condition) and (2) **condition phase**, a categorical (contrast) variable coded as follows: *midluteal baseline visit*, *perimenstrual experimental visit*, and the *medication withdrawal visit*. **Number of lab observations per person.** For the primary contrast between the midluteal and perimenstrual experimental phases, there are 4 observations per person—2 per condition. Based on our preliminary data from the K99 trial (identical experimental manipulation), we anticipate very minimal missing laboratory data (see grant for details) but have estimated that on average each completer participant will miss .25 visits.
3. **Hypothesized Pattern of Effects for Daily and Lab outcomes:** A significant interaction between experimental condition and condition phase is hypothesized for all twelve specified outcomes such that, in the natural withdrawal condition we expect deleterious changes from the midluteal phase to the premenstrual and menstrual phases (due to corresponding hormone withdrawal), but in the hormone stabilization condition we expect no deleterious changes (or less severe changes) from the midluteal to the premenstrual and menstrual phases (since hormone withdrawal is prevented).

Testing Associations Between Mediators and Suicide Outcomes: Aim 1 and 2 next require that we evaluate the day-to-day or week-to-week associations between single mediators (listed above) and suicide outcome variables on the same day or visit. This will be carried out in similar multilevel models as above, predicting each of the three primary suicide outcomes from person-centered values for each of the 9 mediators (listed above).

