Statistical Analysis Plan

Project Title: Cyclical Neuroactive Steroid Changes, Arousal, and Proximal Suicide Risk: An Experimental Approach

Principal Investigator: [name]

Approved as of September 24, 2019

Statistical Analysis Plan

There are twelve total outcomes, which are specified and numbered (#) below. In order to better set up the power analysis details that follow, I have noted the anticipated intra-class correlations for each outcome (in red) and note from which preliminary data these estimates arise.

OUTCOME SPECIFICATION

- Suicide Outcome Variables. In our primary analyses, proximal suicide risk will be operationalized as (1) daily severity of suicidal ideation using the total score on the Adult Suicidal Ideation Questionnaire in the daily survey (ICC=.64 in K99 trial), (2) daily suicidal planning thoughts (dichotomous) on the daily C-SSRS phone risk screen (~10% of days were positive for planning in the K99 trial; ICC=.45 in K99 trial) and (3) daily suicide attempt (dichotomous; aborted, interrupted, or full) on the daily C-SSRS phone risk screen (~1.2% of days were positive for suicide attempt in the K99 trial; ICC=.12 in K99 trial).

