3. Testing Interactive Effects of Hopelessness and Arousal on Suicide Outcomes: Interactions among hopelessness and arousal will be examined as predictors of suicide outcomes and as mediators of the experimental effect. In order to test this, we examine day-to-day interactive effects of daily person-centered hopelessness (noted above) and daily person-centered arousal indices (noted above) predicting same-daily suicide outcomes (noted above). We predict that higher-than-usual hopelessness on a given day will predict greater same-day risk on suicide outcomes, but only when arousal is *also* higher than usual for that individual.

4. Evaluating Mediation Where Appropriate. Finally, each aim indicates that **mediation** will be explored as appropriate. Only when analyses indicate significant effects of the experiment on both the suicide outcome and any mediator, as well as significant associations between the person-centered variable (or interaction variable) and the suicide outcome, we will utilize methods provided by **Bauer**, **Preacher**, **and Gil (2006)** to construct a confidence interval for the level 1 indirect effect of experimental condition (condition X phase) on the suicide outcome via the mediator.

1 R01 MH120843-01 (PI: [name]) POWER ANALYSIS.

With the funds allowed in this four-year grant, we are able to increase our proposed sample size slightly, from 80 to 85 completers, which would allow us to achieve 80% power to detect conventionally small-to-medium sized effects that, in our estimation, are clinically meaningful (i.e., $f^2 = .10$, which would mean that the interaction of condition and phase had uniquely accounted for 10% of the variance in the outcome in the perimenstrual window; Selya et al., 2012, "A Practical Guide to Calculating Cohen's f², a Measure of Local Effect Size"). We posit that if hormone withdrawal (vs. experimental stabilization) does not account for at least 10% of the variance in the outcome during this critical risky window of the menstrual cycle, then this line of research, which involves significant participant burden, is not worth pursuing further.

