- Power in multi-level models has a unique consideration beyond sample size and alpha; it is dependent also on the intraclass correlation (ICC) and its implications for the independence of level-1 observations (i.e., the design effect). High ICCs indicate little variation of the outcome within a given person (i.e., stability of repeated observations within a given person), and suggest that the study's power depends more on the number of higher-level units. Low ICCs indicate high within-person variation within a given person and suggest that the study's power depends more on the number of lower-level units. As the ICC ranges from 0 to 1, the effective n will range from the number of lower-level units to the number of higher-level units. In general, the lower the ICC, the higher the power.
- Snijders and Bosker (1999; *Multilevel Analysis: An Introduction to Basic and Advanced Multilevel Modeling*) provide equations to determine the "Design Effect", which we have used to calculate the "effective lower-level N" based on our expected ICCs for each outcome and our expected number of raw observations with 85 completer participants (including 15% missing at daily level and an average of .25 missing visits per person). Once the design effect and effective N is calculated for a given outcome, one can calculate power to detect a given effect size (in our case, f² = .10) for a given number of these *effective* lower-level units (observations or visits)— see Table below for estimates for the current design. We considered a single fixed regression coefficient in a model with 3 predictors, one-tailed test, alpha=.004.
 

Variable	Measureme nt interval	ICC	Upper-Level Sample Size	Effective Lower- Level N based on ICC and Design Effect Equation	Power Achieved to detect f ² = .10
Suicidal Ideation	Daily	.64	85	130	.81
Suicidal Planning	Daily	.45	85	180	.93
Suicide Attempt	Daily	.12	85	542	.99
Beck Hopelessness Scale	Daily	.32	85	244	.98
Brief Agitation Measure	Daily	.26	85	292	.99
Accelerometer activity	Daily	.54	85	152	.88
Typing Speed Instability	Daily	.38	85	209	.96
HRV withdrawal in the lab	Labs	.50	85	163	.90
PEP shortening in the lab	Labs	.50	85	134	.83
Allopregnanolone in serum	Labs	.29	85	177	.93
PBMC gene expression for 3a- HSD	Labs	.50	85	134	.83
PBMC gene expression for 5a- reductase	Labs	.50	85	134	.83

1 R01 MH120843-01 (PI: [name])

Additional Requested Supplemental Table (2019-08-16)

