Variable	Measurement interval	ICC in pilot data	P value	f-squared	Participants Needed to Achieve 80% Power in Proposed Model*
Suicidal Ideation	Daily	.64	.004	.10	83
Suicidal Planning	Daily	.45	.004	.10	57
Suicide Attempt	Daily	.12	.004	.10	21
Beck Hopelessness Scale	Daily	.32	.004	.10	45
Brief Agitation Measure	Daily	.26	.004	.10	37
Accelerometer activity	Daily	.54	.004	.10	71
Typing Speed Instability	Daily	.38	.004	.10	52
HRV withdrawal in the lab	Labs	.50	.004	.10	74
PEP shortening in the lab	Labs	.50	.004	.10	74
Allopregnanolone in serum	Labs	.29	.004	.10	53
PBMC gene expression for 3a-HSD	Labs	.50	.004	.10	74
PBMC gene expression for 5a-reductase	Labs	.50	.004	.10	74

[figure not shown]
*First, we calculated the number of observations required using a normal GLM framework (non-multilevel). Then, we calculated how many participants would be required to achieve that number of adjusted observations after penalizing for the anticipated design effect, which adjusts for the degree of non-independence in values (Snijders & Bosker, 1999) using the anticipated intraclass correlation (ICC) for each outcome. Anticipated ICCs are based on pilot data from prior studies.

1 R01 MH120843-01 (PI: [name])

• Plotting Power Across a Range of Participant-Level Sample Sizes. In addition, one can use the design effect equation to calculate expected power for a range of upper-level sample sizes (i.e., number of participants) adjusting for the most stringent design effect at that repeated measures interval (based on ICC=.64 for daily variables); see the figures below for power estimates across a range of possible participant-level sample sizes.

Effect of Number of Completer Participants on Power to Detect Effects of Intervention on Daily Outcomes in a Two-Level Regression Model (Days Nested within Participants)

[figure not shown]
(Inputs: Fixed Regression Model, 3 predictors, Bonferroni-corrected alpha=.004, Corrected for Design Effect Based on largest expected ICC of .64, and assuming 15% missingness per person)

Number of Completer Participants (Level-2 Units)

Effect of Number of Completer Participants on Power to Detect Effects of Intervention on Laboratory Outcomes in a Two-Level Regression Model (Visits Nested within Participants)

(Inputs: Fixed Regression Model, 3 predictors, Bonferroni-corrected alpha=.004, Corrected for "Design Effect" Based on largest expected ICC for lab visits .50, and assuming an average of .25 missing visits per person)

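### Step 1 multiplicity is a single-step Bonferroni level given only as a power input; Holm would hold the same error rate with more power, and the mediator-outcome path has no stated level

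*SAP*

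**What the plan says.** The SAP's outcome specification opens: "There are twelve total outcomes, which are specified and numbered (#) below". They are three suicide outcomes and nine mediators. For step 1, the test of the experiment on each outcome, protocol section 10.0 (and the SAP in the same terms) states: "A significant interaction between experimental condition and condition phase is hypothesized for all twelve specified outcomes".

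A significance level appears only in the SAP's power section. The text before the power table reads: "We considered a single fixed regression coefficient in a model with 3 predictors, one-tailed test, alpha=.004". The inputs to the power figures read: "Fixed Regression Model, 3 predictors, Bonferroni-corrected alpha=.004". The supplemental table repeats .004 for every outcome. The protocol gives no level for these tests.

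The analytic steps in both documents refer to significance without a level, sidedness or procedure. Step 2 relates each of the nine mediators to each of the three suicide outcomes. Step 3 adds hopelessness-by-arousal interactions. Step 4 builds an interval for the indirect effect only if three results are significant: the experiment on the outcome, the experiment on the mediator, and the mediator-outcome association. No confidence level is given for that interval.

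**The concern.** Single-step Bonferroni gives up most power when many of the tested effects are real, and that is what the plan expects. Holm's procedure controls the same family-wise error under any dependence and rejects everything Bonferroni rejects. Step 4 makes the loss matter more. Each outcome was powered on its own, but a mediation interval needs an outcome and a mediator to pass together, and that joint probability can fall below 80% even when each test alone exceeds it.

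The second matter is the part of the mediation chain that step 1 does not touch. Apart from 1a, the predictions under Aims 1 and 2 are mediation hypotheses (protocol section 3.0). The step 1 tests screen the path from experiment to mediator. The path from mediator to outcome is tested many times at a level nobody has written down.

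**Working it through.** **Reproducing the plan's figures.** The .004 is .05/12 = .00417, rounded. The SAP's effective N is n·m / (1 + (m − 1)·ICC), with n = 85 completers.

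- Ideation: m = 24 daily observations, ICC .64. 85 × 24 = 2040; 1 + 23 × .64 = 15.72; 2040/15.72 = 129.8 (SAP: 130). Noncentrality √(.10 × 130) = 3.61; one-sided .004 critical t on 126 df = 2.69; power .817 (SAP: .81).
- PEP: m = 4 − .25 = 3.75 visits, ICC .50. 85 × 3.75 = 318.75; 1 + 2.75 × .50 = 2.375; 318.75/2.375 = 134.2 (SAP: 134). Power .831 (SAP: .83).

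All twelve stated powers reproduce within two points from their stated effective N, one-sided. One effective N does not reproduce: HRV is stated as 163, but its ICC and visit count give 134. The stated powers are used as they stand below.

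**Holm against Bonferroni.** Each outcome's test statistic is given mean z(power) + z(.996), where z(.996) = 2.65. Ideation: .88 + 2.65 = 3.53. PEP: .95 + 2.65 = 3.61 (.954 + 2.652). For each scenario, 200,000 sets of twelve one-sided normal statistics were drawn with inter-test correlation 0, .3 and .6 (assumed; the documents give none). Bonferroni compares every p with .05/12. Holm compares the ordered p values with .05/12, .05/11, …, .05/1 and stops at the first failure. The ranges run over the three correlations.

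| Effects that are real | Ideation: Bonferroni | Ideation: Holm | Ideation and PEP: Bonferroni | Ideation and PEP: Holm | Family-wise error: Bonferroni | Family-wise error: Holm |
|---|---|---|---|---|---|---|
| All 12 | .81 | .94–.96 | .68–.73 | .92–.93 | – | – |
| 6 (ideation, hopelessness, agitation, PEP, ALLO, one enzyme) | .81 | .85–.86 | .68–.73 | .75–.79 | .019–.025 | .035–.047 |
| 2 (ideation, PEP) | .81 | .82 | .68–.73 | .69–.74 | .027–.041 | .032–.047 |
| 1 (ideation) | .81 | .81 | – | – | .029–.045 | .031–.048 |

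A hand check of the pair at zero correlation: .81 × .83 = .67 at exactly .004, or .68 at .00417. Simulating t statistics from f² = .10 and the stated effective Ns gives .93–.94 for the pair under Holm with all twelve real, so the overall range is .92–.94. Both enzyme outcomes have the same stated power as PEP (.83), so the all-twelve pair result applies to them too.

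**The mediation chain.** Step 2 has 9 × 3 = 27 associations. Step 3 adds 3 daily arousal indices × 3 outcomes = 9 interactions, or 5 × 3 = 15 if all five arousal indices are used.

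*Null path from experiment to mediator.* If step 4's requirement is run at .004, the chance of any false mediator is at most about 9 × .004 = .036, roughly 4%.

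*Null path from mediator to outcome, Aim 2.* There are 3 mediators × 3 outcomes = 9 paths. The assumptions are: step 1 at .05/12; association tests at two-sided 5%; a 95% delta-method interval that excludes zero when |ab|/√(a² + b²) > 1.96, with a and b in standard-error units; suicide outcomes at the SAP's stated power; correlation 0, .3 and .5; 200,000 draws. The chance of at least one false Aim 2 mediation claim is:

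- all three mediators moved as the SAP assumes: .12–.15;
- ALLO very strong (assumed mean 10), enzymes as the SAP assumes: .16–.20;
- ALLO very strong, enzymes not moved: .11–.12;
- all three very strong (assumed mean 10): .23–.32.

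**The case against.** **The analysis procedure is inferred.** The documents never say that step 1 will be tested at .004. It is a planning input, and a trial sized at .05/12 can still be analysed by Holm. This stands. A reader might infer that the sponsor has committed to Bonferroni for the analysis; the text supports only that no procedure is stated and that the one level given is Bonferroni's.

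**The trial was sized to pay for Bonferroni.** This also stands for single tests: every stated power is .81 or more at .004, so on the SAP's own figures no outcome is underpowered alone. It does not answer the joint requirement in step 4. The largest gains depend on all twelve effects being real, which is the sponsor's hypothesis but the most favourable case. Success on all twelve is not a criterion in either document.

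**Mediation is already gated.** A reader might infer that the mediation results have no error control, or that nine Aim 2 intervals carry a 1 − .95⁹ = .37 chance of a false claim. The documents do not support either. Step 4's three conditions limit false mediators arising from a null experiment-to-mediator path. The .37 supposes that all nine indirect effects always reach an interval and ignores noise in the mediator path. The argument that the administered hormone is a precursor applies to ALLO, not to enzyme mRNA. What remains open is the mediator-outcome path.

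**The family may change.** Protocol section 6.0 replaces the laboratory EKG with the Oura Ring, which bears on the RSA and PEP mediators. The counts of 12 and 27 are the SAP's and may need updating. The case for Holm does not depend on them.

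**Mediation is described as something to explore where appropriate.** An exploratory label is a legitimate answer, though it sits uneasily with aims framed as mechanisms.

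**Conclusion.** The point holds in two parts of unequal weight.

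The main part is Holm for step 1. It keeps family-wise error at or below .05, never rejects less than Bonferroni, and needs no more participants. The gain for ideation alone ranges from nothing, if ideation is the only real effect, to 13–15 points if all twelve are real. For the pair that step 4 needs, it lifts a joint probability below .75 to above .90 under the sponsor's hypothesis. These figures rest on the SAP's stated powers, one-sided tests and assumed correlations.

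The secondary part is a gap in specification. The mediator-outcome tests and the indirect-effect intervals have no level or adjustment. The resulting error is moderate at the SAP's effect sizes and exceeds .20 only when more than one mediator path is very strong. Those figures also rest on an assumed 5% association test, an assumed 95% level, and a delta-method interval standing in for the cited multilevel method.

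**What to change.** In the SAP analytic steps, state that the step 1 outcomes are tested by Holm's procedure at family-wise .05, list the outcomes in the family as it now stands, and state the sidedness. Sidedness matters: at .004 and effective N 130, ideation power is .817 one-sided but .748 two-sided. The cost is a sentence or two. The downside is that Holm gives no single common level for the accompanying confidence intervals.

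For steps 2 to 4, choose one of two courses. Either state the test level and interval level and adjust the mediator-outcome tests and indirect-effect intervals within each aim, which makes the intervals wider; or label the mediation results exploratory, which costs no precision but limits what Aims 1 and 2 can claim.
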